
 
• Concordance between investigator's intra-operative conspicuity assessment of the ureter and BICR assessment for adults with normal renal function or mild renal impairment
 
	
 
• Intra-participant difference in ureter conspicuity for WL versus NIR-F at 30 (<math>\pm 15</math>) min after ASP5354 administration by each BICR reader
 
• CCC, the inter-rater reliability between the investigators and BICR for the WL versus NIR-F at 30 (<math>\pm 15</math>) min after ASP5354 administration
 
• Intra-participant difference in ureter conspicuity for WL at 30 (<math>\pm 15</math>) min versus the average of all NIR-F time points by each BICR reader
 
• CCC, the inter-rater reliability between the investigators and BICR for the WL at 30 (<math>\pm 15</math>) min time point versus the average of all NIR-F time points
 
• Intra-participant difference in ureter conspicuity for WL at 30 (<math>\pm 15</math>) min versus the
 

Objectives	Endpoints
	
end of surgery time point score with NIR-F by each BICR reader
 
 
CCC, the inter-rater reliability between the investigators and BICR for the WL 30 (<math>\pm</math> 15) min time point versus the end of surgery time point score with NIR-F
 

 
Safety of ASP5354
 
	
 
Nature, frequency, severity and causality of TEAEs and serious TEAEs
 
Clinical laboratory tests (hematology, biochemistry and urinalysis)
 
Vital signs
 
Electrocardiograms/cardiac monitoring
 

 
Investigate the pharmacokinetics of ASP5354
 
	
 
Plasma and urine concentrations of ASP5354
 
Ae and Ae%
 

Exploratory	

 
To summarize the investigator's conspicuity assessment with WL of the ureter at each time point
 
	
 
Descriptive summary of left and right ureter conspicuity scores for WL at each time point
 
Descriptive summary of index and non-index ureter conspicuity scores for WL at each time point
 

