### 4.2 Scientific Rationale for Study Design

There are currently no approved imaging agents for ureter identification during open or minimally invasive abdominopelvic/pelvic surgeries. A multicenter, prospective, randomized and open-label study design was chosen to evaluate the intraoperative ureter conspicuity using NIR-F by the operating investigator after administration of ASP5354 compared with ureter conspicuity by WL within each study participant in the WL/NIR-F arm. To reduce the investigator's bias, the WL-only arm is added to cast doubt in the investigator's mind as to whether NIR-F illumination mode will be used for a given participant, which may enhance more consistent behavior (similar due diligence) for evaluation with WL versus NIR-F. Conspicuity assessments in the WL/NIR-F arm will be completed throughout surgery to

evaluate the clinical utility of ASP5354 in ureter visualization. In the WL/NIR-F arm, the first assessment will always be under WL followed by NIR-F assessment. Additionally, a confirmatory blinded independent central review (BICR) will be employed to independently read all WL and NIR-F images for all timepoints for all participants in the WL/NIR-F arm.

ASP5354 has been studied in 2 phase 1 studies in healthy participants and in 1 phase 2 study in participants undergoing laparoscopic or minimally invasive colorectal surgery. ASP5354 was shown to be safe and well tolerated at a single intravenous dose up to 24 mg in the US phase 1 safety and pharmacokinetic study in healthy participants (5354-CL-0001). No treatment-related serious or non-serious AEs were reported in this study. The Japanese phase 1 study (5354-CL-0002) findings are consistent with those observed in the US phase 1 study. No safety issues were reported with no clinically significant changes in vital signs, 12-lead electrocardiogram (ECG), clinical laboratory evaluation or physical examination.

ASP5354 has also been studied in a phase 1 study in participants with mild, moderate or severe renal impairment compared with healthy controls at a 3 mg dose:

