### **9.3.3.2 Additional Secondary Endpoints**

To quantify ureter conspicuity, CEF data will be summarized using descriptive statistics by time point for participants in the mITT population.

The correlation between the CEF assessments and conspicuity values will be investigated. Additional details will be given in the SAP.

The analysis of the primary and key secondary endpoints will be repeated using the following groups of participants. P-values will not be presented. Additional details will be given in the SAP.

- Adolescents
- Adults with moderate renal impairment (eGFR  $\geq 30$  to  $< 60$  mL/min)
- Adults with severe renal impairment (eGFR  $\geq 15$  to  $< 30$  mL/min)
- mITT population

To further characterize the difference of ureter conspicuity under NIR-F vs WL, the frequency and percentage of participants with an average ureter conspicuity assessed by the investigator over all NIR-F time points during surgery at least 1 point higher than the average ureter conspicuity over all WL time points during surgery will be presented. The same analysis will be repeated using a difference of 2, 3 and 4 points. These analyses will be carried out in all cohorts.

The qualitative assessment of index ureter(s) conspicuity scored on a 5-point Likert Scale under WL and NIR-F (1 = None, 2 = Poor, 3 = Sufficient, 4 = Good and 5 = Excellent) performed by a BICR will be summarized descriptively at all time points post-ASP5354 administration. The analysis of the primary and key secondary endpoints will be repeated using the BICR data. This analysis, as well as the descriptive statistics, will be presented within adolescents, adults with moderate renal impairment, adults with severe renal impairment, the ITT population and the mITT population.

The concordance analysis between BICR readers and investigators will be conducted for the ITT population. The hypothesis testing for the primary and key secondary endpoints will be repeated for each separate BICR reader. This will be the primary measure of concordance between the BICR readers and investigator data. A high concordance between the 2 assessments is considered if 2 of 3 BICR readers yield a P value of  $\leq 0.05$ .

The concordance correlation coefficient measuring the agreement between investigator and BICR Likert conspicuity scores will be presented for the following values for each separate BICR reader.

- Difference between NIR-F and WL at the 30-min time point

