The concordance analysis between BICR readers and investigators will be conducted for the ITT population. The hypothesis testing for the primary and key secondary endpoints will be repeated for each separate BICR reader. This will be the primary measure of concordance between the BICR readers and investigator data. A high concordance between the two assessments is considered if 2 of 3 BICR readers yield p-value ≤ 0.05 .

The CCC measuring the agreement between investigator and BICR Likert conspicuity scores will be presented for the following values for each separate BICR reader for the ITT population. This is considered a secondary measure of reliability compared to the hypothesis testing as differences between the raw conspicuity scores of the BICR readers and investigator data may be expected due to the different environments under which conspicuity is assessed.

- Difference between NIR-F and WL at the 30-min time point
- Mean difference between NIR-F across all time points and WL at the 30-min time point
- Difference between NIR-F at the end of surgery time point and WL at the 30-min time point

In addition to the CCC, Kendall's coefficient of concordance along with 95% jackknife CI will be presented in order to assess the agreement across all raters.

BICR data will be listed.

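### The 2-of-3 p-value rule, named as the primary measure of concordance, tests whether central readers replicate the NIR-F effect, not whether they agree with the investigator

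*SAP*

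**What the plan says.** One of the secondary objectives is concordance between the investigator's intraoperative scores and the BICR scores in adults with normal or mildly impaired renal function (Protocol Table 4; SAP 2.1.2.2). For this, SAP 6.4.3 states: "The hypothesis testing for the primary and key secondary endpoints will be repeated for each separate BICR reader". On the role of those tests it says: "This will be the primary measure of concordance between the BICR readers and investigator data". The decision rule follows: "A high concordance between the two assessments is considered if 2 of 3 BICR readers yield p-value" at or below 0.05. Protocol 9.3.3.2 has the same rule: "A high concordance between the 2 assessments is considered if 2 of 3 BICR readers yield a P value" at or below 0.05.

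The repeated hypotheses are those of Protocol 9.1. For H1 and H3 the mean NIR-F minus WL difference is zero, and for H2 the median of the participant-level mean differences is zero. All are two-sided.

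Statistics that do compare raters are also planned. A CCC is computed for each reader against the investigator, but SAP 6.4.3 ranks it lower: "This is considered a secondary measure of reliability compared to the hypothesis testing". The reason given is that raw scores may differ because the viewing environments differ. Kendall's "coefficient of concordance along with 95% jackknife CI will be presented in order to assess the agreement across all raters". Neither statistic has a threshold.

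**The concern.** Concordance between two raters is a property of their paired scores. The 2-of-3 rule uses only the readers' scores, so it would return the same answer whatever the investigator had recorded. What it tests is whether each reader, taken alone, sees a difference between the two illumination modes.

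Two details are also open. The tests are two-sided and the rule names no direction, so readers who favoured WL would satisfy it. Three hypotheses are repeated for each reader, but neither document says whether the 2-of-3 count applies to H1, to any of them or to all.

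At stake is a sentence in the study report. The primary endpoint is scored by an operating surgeon who knows which illumination mode is in use, so independent corroboration carries weight. The report could claim high concordance with that surgeon on a criterion driven by effect size and sample size.

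**Working it through.** **Inputs from the documents.** Difference 1.0, common SD 2.0, correlation 0.2, 90% power, two-sided 0.05, paired t-test, 84 adults randomized (Protocol 9.5.1.1; SAP 3); three readers. The allocation ratio is left to a separate document. Correlations between raters are not given and are assumed below.

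**The plan's own figure.** SD of the difference = 2.0 × √(2 × (1 − 0.2)) = 2.53. Noncentral-t power is 0.899 at n = 69 and 0.903 at n = 70, so 70 is the smallest number giving 90%. This matches the plan if allocation is 5:1 (84 × 5/6 = 70). At 3:1 (n = 63) power is 0.870, and at 2:1 (n = 56) it is 0.828.

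**Rule on H1, readers independent of the investigator and of each other.** With p the power per reader, P(at least 2 of 3) = 3p²(1 − p) + p³.

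| n | p | Rule met |
|---|---|---|
| 56 | 0.828 | 0.921 |
| 63 | 0.870 | 0.954 |
| 70 | 0.903 | 0.974 |

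The mean CCC with the investigator is 0.00 in this setting.

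**Readers correlated with each other.** Readers view the same images, so a reader-reader correlation of 0.8 was also assumed (n = 70, effect 1.0, normal differences, 4,000 simulated trials per row).

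| Investigator-reader correlation | Mean CCC | Rule met | Rule met when investigator's H1 is significant |
|---|---|---|---|
| 0 | 0.00 | 91.3% | 91.1% |
| 0.3 | 0.29 | 91.8% | 93.6% |
| 0.5 | 0.49 | 92.7% | 94.5% |
| 0.8 | 0.79 | 91.5% | 97.0% |

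The unconditional rate is flat while the CCC runs from 0 to 0.79. With the same reader-reader correlation it falls to about 63% at effect 0.7 and 36% at effect 0.5, again whether the CCC is 0.00 or 0.79. The effect size moves the rule; agreement does not.

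**Cases where rule and agreement part company** (n = 70, one common correlation among all four raters).

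| Setting | Mean CCC | Rule met |
|---|---|---|
| Investigator difference 3.0, readers 1.0, correlation 0 | 0.00 | 97.5% |
| Investigator +1.0, readers −1.0, correlation 0 | 0.00 | 97.3% |
| No effect, correlation 0.9 | 0.90 | 4.3% |
| No effect, correlation 0.99 | 0.99 | 4.8% |

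**Other scales.** With an assumed SD of the difference of 1.25, the rule was met in 100% of trials at every correlation tried. With integer 1-to-5 scores (assumed means 2.65 and 3.55, SD of the difference 1.97) and independent raters, it was met in 98% to 99% at n = 56 to 70, again with CCC 0.00.

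**Hypothesis not fixed** (n = 70, independent readers, same effect and SD for all three endpoints, endpoint correlation 0.5 to 0.8).

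| Effect | H1 only | Any of H1–H3 | All of H1–H3 |
|---|---|---|---|
| 1.0 | about 98% | over 99% | 73–77% |
| 0.5 | 31–32% | 51–62% | 2–5% |

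**The case against.** The best defence is that replication is what the sponsor wants. Protocol 4.2 says "a confirmatory blinded independent central review (BICR) will be employed to independently read all WL and NIR-F images", and Protocol Table 4 lists the NIR-F versus WL difference as read by each reader under the concordance objective. Agreement on the conclusion is one sense of concordance, and the SAP gives a reason for expecting raw scores to differ. The criterion is printed beside its label, and the CCC and Kendall's coefficient will be reported in any case.

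Much of this stands. Replication by readers outside the operating room is worth reporting and should be kept. But an expected offset between environments is a reason to estimate that offset. It does not make a p-value without investigator data a measure of agreement, and only the p-value rule carries the words high concordance.

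Four further points are fair, and they limit the illustrations more than the conclusion:

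- The 97.4% assumes no correlation among raters looking at the same ureters, which is a limiting case.
- Among trials where the investigator's own H1 is significant, the rule does respond to agreement when power is lower. At effect 0.5, with investigator-reader correlation 0, 0.3, 0.5 and 0.8, it is met in about 35%, 47%, 58% and 77%; at effect 0.7, in about 64%, 70%, 77% and 86%. Effect size still dominates: 77% at effect 0.5 with a CCC near 0.79 is below the 91.1% at effect 1.0 with a CCC of 0.
- If the fixed testing sequence is also repeated within each reader, the any-of-H1–H3 reading reduces to H1. The documents do not say.
- Direction will be visible in the per-reader summaries, and success in the wrong direction is very unlikely if the true effect favours NIR-F.

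**Conclusion.** The concern holds. The rule tests replication and cannot support a statement of concordance with the investigator. That conclusion follows from which data enter the p-values and needs no assumption. The percentages do rest on assumptions: the planning effect and SD, 70 participants in the WL/NIR-F arm, the assumed correlations, no missing BICR reads and, except for the integer-score case, normal differences.

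At the planned effect the rule is met in roughly 91% to 97% of trials at n = 70, whether agreement is absent or strong. With no effect and near-perfect agreement it is met in under 5%.

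The scope is limited to the label, the ranking above the CCC, the missing direction and the unnamed hypothesis in a secondary analysis. The tests of H1 to H3 and their type I error are untouched. It should be corrected, but it does not threaten the trial's main claim.

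**What to change.** In SAP 6.4.3 and Protocol 9.3.3.2:

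1. Rename the rule as replication of the NIR-F effect by BICR readers, and remove the terms high concordance and primary measure of concordance from it.
2. Require each counted reader's difference to favour NIR-F.
3. State before database lock which hypothesis the count applies to, for example H1 with H2 and H3 reported per reader, and whether the fixed sequence is repeated within readers.
4. Base any concordance statement on the per-reader CCC with a 95% confidence interval, beside the mean investigator-minus-reader difference, which shows any viewing-environment offset.
5. Keep Kendall's coefficient as a supplement only. It also reflects agreement among the readers: with reader-reader correlation 0.8 and investigator-reader correlation 0 it averages 0.54 over the four raters.

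The cost is wording plus two small outputs per reader, with no new data. The protocol wording change needs ethics committee approval (Protocol 10.1.1). If the database is already locked, the change should be documented in the study report, as SAP 1 provides.

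There are downsides. Concordance may look less favourable, and no CCC threshold is proposed, so agreement would be described and not declared. The CCC can also be low when true differences vary little between participants. With an assumed true difference of mean 2 and SD 0.3, and rater error SD 0.5 with rounding, raters are within one point in 95% of cases yet the CCC is 0.21. This is why it should be read with the mean difference.

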6.4.4 Analysis of Exploratory Efficacy Endpoints

The exploratory efficacy endpoints are listed in section [5.4](#).

Descriptive statistics will be used to summarize the ureter conspicuity by time point under WL for both the left and right ureters of participants in the ITT and mITT population. In addition, the same descriptive statistics summary will be applied for the ureter conspicuity under WL for both index and non-index ureters in the ITT and mITT populations.

Inter- and intra-rater reliability within the BICR readers will be measured using the assessments at the 30-min time point for the ITT population and will be assessed using an ICC with a 95% CI. Inter-rater reliability of the differences between the 30-min WL and 30-min NIR-F values as well as the raw values under WL and NIR-F will be assessed. Intra-rater reliability of the repeat readings of the 30-min WL and 30-min NIR-F images will also be assessed. Intra-rater reliability of the differences between the 30-min WL and 30-min NIR-F values will also be assessed. ICC will be calculated using Shrout-Fleiss formulae for estimation of inter- and intra-rater reliability (agreement) (ICC [2, 1], as defined in Qin et al., 2019). As a primary indicator, ICC for inter-rater and intra-rater (also called test-retest) reliability will be assessed using separate ANOVA models. Inter-rater reliability will be assessed using a random-effects ANOVA, estimating random effects of BICR reader and image. Intra-rater reliability will be assessed using a mixed-effect ANOVA, estimating random effects of BICR reader, image and fixed effect of time point. Parameters from the outputs obtained in these analyses will be used in the formula below to calculate two ICCs (for inter-and intra-rater reliability):

$$\frac{MS_B - MS_E}{MS_B + (k - 1)MS_E + k/n(MS_W - MS_E)}$$

where MS_B = mean squares for image (for inter-rater reliability), MS_E = mean square for error, n = number of images (for inter-rater reliability), k = number of surgeon raters (for inter-rater reliability), and MS_W = mean square for rater (for inter-rater reliability).

In the case of intra-rater reliability, the above formula has a slightly different interpretation: MS_W = mean square for time point and k = number of time points (here 2) and n = number of raters multiplied by the number of images.

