5.4 Exploratory Efficacy Endpoints

The exploratory efficacy endpoints are as follows:

- Descriptive summary of left and right ureter conspicuity scores for WL at each time point
- Descriptive summary of index and non-index ureter conspicuity scores for WL at each time point
- Intraclass correlation coefficient (ICC), the inter-rater reliability among BICR readers on the intra-participant difference in ureter conspicuity for WL versus NIR-F at 30 (± 15) after ASP5354 administration
- ICC, the inter-rater reliability among BICR readers on the scoring in ureter conspicuity for the WL and NIR-F at 30 (± 15) min after ASP5354 administration

- ICC, the intra-rater reliability within each BICR reader on the intra-participant difference in ureter conspicuity for WL versus NIR-F at 30 (± 15) min after ASP5354 administration
- ICC, the intra-rater reliability within each BICR reader on the scoring in ureter conspicuity for the WL and NIR-F at 30 (± 15) min after ASP5354 administration

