In analyses of BICR data where BICR readers assess the same 30-min image twice, the second reading will only be used in the analysis of intra-rater reliability within BICR readers. In other analyses of BICR data, only the first assessment will be analyzed.

All safety summaries will be presented for the following groups unless otherwise specified:

- All participants who received ASP5354
- Adult participants (≥ 18 years)
- Adult participants randomized to the WL/NIR-F arm
- Adult participants randomized to the WL-only arm
- Adult and adolescent participants enrolled/randomized to the WL/NIR-F arm
- Adolescent participants (12 to < 18 years)
- Participants with moderate renal impairment (eGFR ≥ 30 to < 60 mL/min)
- Participants with severe renal impairment (eGFR ≥ 15 to < 30 mL/min)

For participants who re-screen and have a new participant ID assigned, only data collected under the new participant ID will be used in the analysis. Data collected under the old participant ID will be listed only.

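### The intra-rater ICC in SAP 6.4.4 is pooled over readers and its between-image mean square is undefined, so it does not deliver the endpoint of reliability within each BICR reader

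*SAP*

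**What the plan says.** The endpoint is worded per reader. SAP 5.4 lists "ICC, the intra-rater reliability within each BICR reader on the scoring in ureter conspicuity", with a parallel endpoint for the NIR-F minus WL difference. Protocol Table 4 has the same wording, and protocol 9.3.4 leaves the details to the SAP.

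SAP 6.4.4 gives the method. The intra-rater model is a single mixed ANOVA "estimating random effects of BICR reader, image and fixed effect of time point". Its mean squares enter the Shrout-Fleiss ICC(2,1) formula "to calculate two ICCs (for inter-and intra-rater reliability"), that is, one of each kind per measure. For the intra-rater case the section redefines three symbols: "MS_W = mean square for time point and k = number of time points (here 2"), and "n = number of raters multiplied by the number of images". The fourth is defined only as "MS_B = mean squares for image (for inter-rater reliability"). No reader-by-image term is listed.

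SAP 6.1 says of images read twice that "the second reading will only be used in the analysis of intra-rater reliability within BICR readers". There are three readers, as SAP 6.4.3 shows: "A high concordance between the two assessments is considered if 2 of 3 BICR readers yield p-value" at or below 0.05. The same section treats a primary reader and a backup as one reader.

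**The concern.** The analysis does not answer the question in the endpoint. A pooled coefficient cannot say whether each reader is repeatable, and no other analysis in either document does so. The per-reader hypothesis tests and CCCs in SAP 6.4.3 compare readers with investigators; they are not test-retest measures.

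The formula also cannot be programmed without a guess. ICC(2,1) is built for a two-way layout of targets by readings. Here the data have three factors (reader, image, reading occasion), and MS_B, n and k must all refer to the same target. With n equal to readers times images, the target looks like the reader-image pair; the only stated MS_B is for the image.

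At stake is how much weight the central review can bear. The investigator gives the NIR-F score after the assignment is revealed, so the BICR is an important check on it. Because high concordance is declared on two of three readers, a single reader's repeatability is useful to know.

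**Working it through.** The documents give no ICC, target value or variance component, so there is no figure to reproduce.

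**Inputs**
- From the SAP: 3 readers, 2 readings, k = 2, n = readers × images, additive model.
- Assumed: 70 re-read images, so n = 210. With an SD of differences of 2√(2(1 − 0.2)) = 2.53, 70 participants give 90.3% power (69 give 89.9%), and 70 is 5/6 of 84. The allocation ratio and the number of images read twice are not stated. Runs with 50 and 84 images gave the same pattern.
- Assumed: variances V_img (image), V_rdr (reader), V_ri (reader-by-image), V_err (re-read error), with no drift between readings.

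**Target.** Within one reader, the stable reader-by-image part is signal: ICC = (V_img + V_ri)/(V_img + V_ri + V_err).

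**SAP formula.** (MS_B − MS_E)/(MS_B + MS_E + (2/210)(MS_W − MS_E)). The last term is below 0.005 in size in these cases.

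**Reading A: MS_B is the image mean square of the additive model**
- MS_B has expectation 6V_img + 2V_ri + V_err, because each image carries 3 × 2 = 6 scores.
- The residual has 420 − 1 − 69 − 2 − 1 = 347 df, of which 2 × 69 = 138 carry V_ri. So MS_E has expectation V_err + 2(138/347)V_ri = V_err + 0.795V_ri.
- V_img = 1, V_err = 1, others 0 (true 0.50): (7 − 1)/(7 + 1) = 0.75; simulation 0.74. The inflation arises because a mean square over six scores is combined with k = 2.
- V_img = 1, V_ri = 0.5, V_err = 0 (true 1.00): (7 − 0.398)/(7 + 0.398 − 0.004) = 0.89; simulation 0.89. Here stable disagreement is counted as re-read error.

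The two effects oppose each other, so the net direction depends on the variances.

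**Reading B: MS_B is the mean square over reader-image cells, MS_E the residual after cells**
- MS_B has expectation V_err + 2V_ri + 2V_img(207/209) + 2V_rdr(140/209), so differences between reader means count as signal.

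**Reading C: MS_B is image within reader, MS_E the residual after cells**
- MS_B has expectation 2V_img + 2V_ri + V_err, which returns the target when readers share the same V_err.

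**All three on one case** (V_img 0.64, V_rdr 0.49, V_ri 0.16, V_err 0.49), true value 0.80/1.29 = 0.62:
- A: MS_B = 3.84 + 0.32 + 0.49 = 4.65; MS_E = 0.49 + 0.127 = 0.617; 4.033/5.267 = 0.77.
- B: MS_B = 0.49 + 0.32 + 1.268 + 0.656 = 2.734; 2.244/3.224 = 0.70.
- C: MS_B = 2.09; 1.60/2.58 = 0.62.

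**One weak reader.** A and B are simulation means (2,000 runs). C is V/(V + mean V_err), with V = V_img + V_ri.

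| True ICC per reader | A | B | C |
|---|---|---|---|
| 0.90, 0.90, 0.50 | 0.80 | 0.73 | 1.3/(1.3 + 0.530) = 0.71 |
| 0.90, 0.90, 0.40 | 0.76 | 0.65 | 1.3/(1.3 + 0.746) = 0.64 |
| 0.90, 0.90, 0.30 | 0.78 | 0.54 | 1/(1 + 0.852) = 0.54 |

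Rows 1 and 2 use V_img 1, V_rdr 0.2, V_ri 0.3 and V_err of 0.144, 0.144 and then 1.30 or 1.95. Row 3 uses V_img 1, no reader or reader-by-image variance, and V_err 0.111, 0.111, 2.333. ICC(2,1) run separately by reader returned about 0.90, 0.90 and then 0.50, 0.39 and 0.30. Rounding scores to the 1–5 scale left the pattern unchanged (row 1: 0.84, 0.84, 0.45 by reader, against 0.78 under A and 0.70 under B).

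**The case against.** The best defence is that the SAP is incomplete and not shown to be wrong. A reader term in the model and n = readers × images both fit reading C, which is unbiased for equally repeatable readers. That stands, and it rules out a stronger claim that a reader might infer: that the formula fails on every interpretation, or is biased in a known direction. Two qualifications apply. Reading C needs a residual taken after reader-image cells, and the listed additive model does not give one. With the additive residual, perfectly repeatable readers with V_img = 1 and V_ri = 0.5 would score (3 − 0.398)/(3 + 0.398 − 0.004) = 0.77. And reading C is still pooled.

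It is also fair that the endpoint is exploratory, that no threshold or decision uses this ICC, and that SAP 6.4.3 makes the per-reader hypothesis tests the primary concordance measure, with per-reader CCCs and descriptive summaries beside them. So the documents do not support the inference that the BICR evidence as a whole is unsound. Those analyses do not measure test-retest reliability, however, so the gap in this endpoint remains.

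Finally, the variance components are assumptions. The figures show what can happen, not what will.

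**Conclusion.** The point holds. Two parts follow from the text alone: the endpoint is per reader while the planned ICC is pooled, and MS_B is undefined for the intra-rater case. The size of any error depends on the reading chosen and on unknown variances. The literal reading can inflate (0.50 to about 0.75) or deflate (1.00 to 0.89); the cell reading inflates when reader means differ (0.62 to 0.70 in the worked case); the image-within-reader reading is unbiased for equal readers. Masking of one weak reader does not depend on the reading: 0.90, 0.90 and 0.50 appear as one value between 0.71 and 0.80. These figures assume 3 readers, 70 images read twice and the stated variances. It would go too far to infer any effect on the trial's main result: the primary and key secondary tests do not use this coefficient.

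**What to change.** In SAP 6.4.4, replace the pooled intra-rater calculation. For each measure (WL, NIR-F and their difference), compute ICC(2,1) separately for each reader, with:
- n = images read twice by that reader, and k = 2 readings;
- MS_B = image mean square, MS_W = reading-occasion mean square and MS_E = residual, all within that reader;
- a 95% CI for each value.

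Keep the existing formula for inter-rater reliability only. State how many images are read twice, and flag any result where a primary reader and a backup are merged, since that value may mix two people.

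The cost is a few lines of text and a by-reader run on data already planned. The per-reader intervals are wider. As a guide, the one-way F interval at an ICC of 0.8 starts from F = 1.8/0.2 = 9, with limits (x − 1)/(x + 1) for x = 9/F(0.975; n − 1, n) and x = 9 × F(0.975; n, n − 1). It gives 0.70 to 0.87 with 70 images, 0.50 to 0.93 with 14 and 0.27 to 0.96 with 7. SAP section 1 allows updates before database lock; after lock, the change can be documented in the CSR.
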